### 11.1. ADVERSE EVENTS

The Medical Dictionary for Regulatory Activities (MedDRA) will be used for coding AEs. An AE (classified as preferred term) occurring after initiation of study drug will be counted as a treatment emergent AE (TEAE) either if it is not present at baseline or if it is present at baseline but increased in severity after initiation of study drug. If more than one AE with the same preferred term was reported pre-baseline, then the report with the greatest intensity is used as the benchmark for comparison to post-baseline reports of events with that preferred term.

The number (percentage) of patients reporting TEAEs for each preferred term will be tabulated by system-organ class, by system-organ class and severity, and by system-organ class and relationship to study drug. If more than one event occurred with the same preferred term for the same patient, the patient will be counted only once for that preferred term using the most severe or related occurrence for the summary by severity, or relationship to study drug, respectively. An individual patient will be counted only once for any specific preferred term regardless of the number of times that preferred term occurred for that patient.

The incidence of SAEs and AEs leading to discontinuation of study drug will be summarized separately by system-organ class, preferred term for the safety population.

Listings will be presented for patients with SAEs/AEs leading to a discontinuation or death.

### 11.2. LABORATORY PARAMETERS

Serum chemistry including serum creatinine, triglycerides, lipase, total cholesterol, high density lipoprotein (HDL), low density lipoprotein (LDL), very low density lipoprotein (VLDL), alanine transaminase/serum glutamic-pyruvic transaminase (ALT/SGPT), aspartate transaminase/serum glutamic oxaloacetic transaminase (AST/SGOT), total bilirubin, lactate dehydrogenase, blood urea nitrogen, sodium, potassium, calcium, and magnesium will be assessed at screening and then every 24 hours (+/- 1 hour) during study drug administration up to 96 hours (or at the termination of study drug infusion if less than the 24 hour timepoint). A blood sample will also be drawn 4 hours (+/- 30 minutes) after termination of study drug infusion.

Hematology including red blood cells, hemoglobin, hematocrit, white blood cells, and platelets will be collected only at screening.

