4.4.1. Withdrawal from Study Medication

The following data will be collected within 1 hour (+ 30 minutes) after the end of study drug infusion, provided the patient or parent or legal guardian did not withdraw the right for the Sponsor to use the patient's data:

- Physical examination
- Vital signs
- Serum chemistry including serum creatinine, triglycerides, lipase, total cholesterol, HDL, LDL, VLDL, ALT/SGPT, AST/SGOT, total bilirubin, lactate dehydrogenase, blood urea nitrogen, sodium, potassium, calcium, and magnesium
- AEs / SAEs
- Concomitant medications including oral and/or IV antihypertensive administration
- PK blood sample

In addition, any PK samples collected will be analyzed. The patient should continue to be followed through the follow-up phase of the study.

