BP and HR will be measured and PK samples will be obtained throughout this period. Multiple, timed BP measurements are required to be taken prior to and following PK sample collection. Accurate and well-timed BP readings will also be necessary to capture the patient's response to infusion rate adjustments during the first 30 minute period and through study drug termination. To accommodate the frequency and precision required for this, physiologic blood pressure monitoring will be carried out using a peripheral arterial line, to allow for real-time heart rate and BP sampling while obtaining PK samples throughout the course of study drug titration and through the follow-up period. It is essential that the clock time of infusion pump devices, blood pressure monitors and clocks used to record the time of the PK sample be synchronized. Serum chemistry (Sections 6.1 and 6.3) will be assessed. Concomitant medications, AEs and SAEs will be monitored throughout the study period and concludes on day 7 in the follow-up period. If appropriate, patients will be transitioned to oral therapy one hour prior to termination of clevidipine (Section 6.5.3).

The follow-up period is divided into these time points following study drug termination: 1 hour follow-up, 12 hour follow-up, 24 hour follow-up and 7 day follow-up. The 1 hour time point starts from discontinuation of study drug until 1 hour (+ 30 minutes) post study drug termination. During this period, concomitant medications, serum chemistry, BP, HR and PK samples (PK Samples 7, 8, 9, 10 – Table 1) will be obtained and AE and SAEs will continue to be monitored and recorded. During the 12 hour time point (+ 30 minutes) period BP, concomitant medications, AEs and SAEs will continue to be monitored and recorded. During the 24 hour (+ 30 minutes) time point period, concomitant medications, AE and SAEs will be monitored and recorded. The 7 day (+1 day) follow-up time point period occurs on day 7 (+1 day) post study drug termination. The 7 days follow-up will occur by phone (if applicable) to monitor and record AE and SAEs.

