⁴ BP and HR will be recorded every 1.5 minutes (+ 30 second window where a PK sample is required) for a period of at least 30 minutes, every 10 minutes for the next hour, every 30 minutes for the next 2 hours and every 1 hour until study drug is terminated (up to 96 hours). BP and HR will also be recorded immediately before each PK blood draw (Table 1) is obtained.

⁵ If a dose adjustment is indicated, BP and HR should be recorded just prior to each study drug dose change as well as every 1.5 minutes for 15 minutes after the dose adjustment, then return to the BP assessment schedule just prior to the dose adjustment.

clevidipine Confidential

⁶ BP and HR will be recorded every 1 hour until study drug has been stopped for 12 hours post-study drug termination.

⁹ Beyond the first 30-minute treatment period, it may be necessary to alter the desired SBP target range over the course of the remaining treatment period. Any changes in the target range will be captured in the case report form (eCRF).

¹⁰ The 7 day (+1 day) follow-up can occur by phone, if applicable.

¹¹. Serum chemistry within 1 (+30 minutes) hour after study drug termination

¹². AE and SAE reporting will be from time of consent through 7 days day) following termination of study drug infusion.

Table 1: PK sampling times

| Sample | Time point |
|----------------------|---|
| 1 | Up to 30 minutes prior to start of clevidipine infusion |
| 2 | 1.5 minutes post initiation of clevidipine infusion (before first dose titration) |
| 3 | 1.5 minutes after first dose titration (must be performed before proceeding to second dose titration) |
| 4 | Once target SBP range is reached or 30 minutes after the initiation of clevidipine infusion, whichever comes first |
| 5 (if applicable) | If transition to an additional antihypertensive is desired and concurrent administration is needed, a sample should be taken right before beginning administration of the additional antihypertensive agent |
| 6 | Right before termination of the clevidipine infusion |
| 7 | 0.5 minutes post termination of the clevidipine infusion |
| 8 | 3 minutes post termination of the clevidipine infusion |
| 9 | 15 minutes post termination of clevidipine infusion |
| 10 | 1 hour (+30 minutes) post final termination of the clevidipine infusion |

⁷ Clevidipine administered as a continuous IV infusion.

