6.5.4. Follow-Up Period

The follow-up period is divided into these time points following study drug termination: The 1 hour time point is from study drug termination to 1 hour (+ 30 minutes) post study drug termination. The 12 hour, 24 hour and 7 day time points occur from 12 hours (+ 30 minutes), 24 hours (+ 30 minutes) and 7 days (+/- 1 day) post study drug termination, respectively. During this phase of the study, 4 PK samples will be taken: PK Sample 7 taken 0.5 minutes post study drug termination, PK Sample 8 taken at 3 minutes post study drug termination, PK Sample 9 taken at 15 minutes post study drug termination and PK Sample 10 taken 1 hour post study drug initiation. For all samples, BP and HR will be measured immediately followed by the PK blood draw, which will be taken from the indwelling arterial line within a 30 second window after BP and HR are obtained.

The following assessments will be performed during the Follow-up Period:

- BP and HR
 - measured at least every 15 min. until study drug has been stopped for 60 min. then at least every hour until study drug has been stopped for 12 hours post study drug termination
- PK Samples 7, 8, 9, 10: taken at 0.5 min. (PK Sample 7), 3 mins (PK Sample 8), 15 min (PK Sample 9) and 1 hours (+ 30 minutes) (PK Sample 10) post study drug termination (taken in the order below)
 - o BP and HR
 - o PK Sample

- BP and HR to continue at least every 15 min. until study drug has been stopped for 60 min. then at least every hour until study drug has been stopped for 12 hours post study drug termination, as instructed above
- Serum chemistry (Section 6.3) within 1 hour (+ 30 minutes) of termination of study drug.
- Concomitant medications through 24 hours post study drug termination (update if ongoing medications through day 7)
- AEs and SAEs through 24 hours post study drug termination (update if ongoing AEs through day 7 [+1 day])

Participation in the study is complete after day 7 follow-up visit is completed; all ongoing SAEs have been followed to resolution.

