- 9 Beyond the first 30-minute treatment period, it may be necessary to alter the desired SBP target range over the course of the remaining treatment period. Any changes in the target range will be captured in the case report form (eCRF).
-  The 7 day (+1 day) follow-up can occur by phone, if applicable.
- . Serum chemistry within 1 (+30 minutes) hour after study drug termination
- 12. AE and SAE reporting will be from time of consent through 7 days day) following termination of study drug infusion.

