### 11.2.2. Laboratory analysis

Descriptive statistics for the values of serum chemistry as well as relative and percent changes from baseline will be summarized by time point: baseline (screening), every 24 hours during study drug administration (or at the termination of study drug infusion if less than the 24 hours timepoint), and at 4 hours after termination of study drug infusion. Values for each hematology parameter will be presented only at screening.

Values of laboratory tests are considered potentially clinically significant (PCS) if they meet the PCS criteria listed in Table 3. The number (percentage) of patients with post-baseline PCS values who do not have PCS values at baseline will be analyzed for the safety population. For calculation of the percentages, the denominator is based on the number of patients with non-PCS baseline values and at least one post-baseline assessment for the laboratory parameter being analyzed. The numerator is based on patients from the denominator who had at least one post-baseline PCS value for the laboratory parameter being analyzed. A supportive listing of patients with all PCS values will be provided including the patient number, age, gender, treatment time. Both raw and standardized pre-baseline, baseline, and post-baseline values and normal ranges will be in the listing, along with the standardized abnormality flag.

Table 3: Criteria for Potentially Clinically Significant Abnormal Laboratory
Tests

Parameter	Low Limit	High Limit					
Serum Chemistry							
Serum Creatinine, mg/dL	_	≥2 mg/dL					
Triglycerides, mg/dL	_	≥300 mg/dL					
Lipase, U/L	_	≥3 × ULN					
Total Cholesterol, mg/dL	_	≥300 mg/dL					
HDL, mg/dL	_	≤20 mg/dL					
LDL, mg/dL	_	≥200 mg/dL					
VLDL, mg/dL	_	≥100 mg/dL					
Alanine Transaminase (ALT/SGPT), U/L	_	≥3 × ULN					
Aspartate Transaminase (AST/SGOT), U/L	_	≥3 × ULN					
Total Bilirubin, mg/dL	_	≥1.5 × ULN					
Lactate Dehydrogenase (LDH)	_	≥3 × ULN					
Blood Urea Nitrogen (BUN), mg/dL	_	≥1.5 × ULN					
Electrolytes	Electrolytes						
Sodium, mg/L	≤0.9 × LLN	≥1.1 × ULN					
Potassium, mg/L	≤0.9 × LLN	≥1.1 × ULN					
Calcium, mg/dL	≤0.9 × LLN	≥1.1 × ULN					
Magnesium	≤0.9 × LLN	≥1.1 × ULN					

LLN: Lower limit of the standard reference (normal) range.

ULN: Upper limit of the standard reference (normal) range.

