### 20.1.2. Visit windows for laboratory parameters

The following are the time windows (in hours) used for the summary tables of laboratory parameters during the study drug infusion.

>0 to <36 for 24 ≥36 to <60 for 48 ≥60 to <84 for 72 >84 to <106 for 96

The following are the windows used for the data measured post the cessation of study drug infusion.

 $\geq$ 1 h post-infusion to  $\leq$ 5 h post-infusion for 4 hours post-infusion

For example, if there is no 48-h measurement, the data measured in the time window between 36 h and 60 h will be considered. The values measured closest to 48 h in the window will be considered as the 48-hrs. value. If two values are both equally close to 48 h in the window, the one measured in the earlier time will be used for the analysis. The assessment at 48-h will be considered missing if there are no assessments in the time window from 36 h to 60 h

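### The SAP tabulates post-infusion chemistry at 4 hours (window 1 to 5 h), but the schedule has it drawn within 1 hour (+30 min), so compliant samples drop out of that row or carry the wrong time

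*SAP*

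**What the plan says.** **The schedule.** Protocol 6.5.4 lists "Serum chemistry (Section 6.3) within 1 hour (+ 30 minutes) of termination of study drug". Protocol 4.4.1, for patients who stop study medication, introduces a list that includes serum chemistry with "The following data will be collected within 1 hour (+ 30 minutes) after the end of study drug infusion". Footnote 11 to the schedule in Protocol 6.1 gives the same timing, and SAP Table 1 repeats it in its own footnote 11: "Serum chemistry within 1 (+30 minutes) hour after study drug termination". Protocol Section 6 fixes where the interval begins: "The 1 hour time point starts from discontinuation of study drug until 1 hour (+ 30 minutes) post study drug termination". Neither schedule contains a 4-hour chemistry draw.

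**The analysis.** SAP 11.2 describes a different sample: "A blood sample will also be drawn 4 hours (+/- 30 minutes) after termination of study drug infusion". SAP 11.2.2 lists the time points to be summarised and ends with "and at 4 hours after termination of study drug infusion"; it has no 1-hour post-infusion point. In SAP 20.1.2 the only post-infusion laboratory window opens at 1 h and closes at "5 h post-infusion for 4 hours post-infusion". The 24, 48, 72 and 96 h windows in that section are introduced as applying while the drug is being infused.

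**Declared changes.** The SAP cites Protocol Version 3, the version reviewed here. Its Section 18 declares one departure from the protocol, on vital signs, and nothing on the timing of chemistry.

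**The concern.** Sites draw blood by the protocol schedule, and programmers build tables from the SAP windows. Here the two describe different samples. The 4-hour point stands in three SAP sections, one of them a window meant to be programmed, so it is not a stray slip in one sentence. It conflicts both with the protocol and with the SAP's own Table 1.

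Protocol 3.3 lists the safety of prolonged infusion, judged in part by clinical laboratory parameters, among the primary endpoints. Protocol 1.2.3 relies on blood chemistry monitoring to limit the risks of the lipid formulation, and the affected panel includes triglycerides, lipase and cholesterol. Followed as written, the SAP gives a post-infusion row of values, changes and percent changes from baseline that leaves out compliant samples, reports them at a time when no blood was scheduled, or does both.

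**Working it through.** The plan gives no figure to reproduce here. The check compares time intervals, in hours after the infusion stops.

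**Inputs**
- Compliant draw, A = [0, 1.5]: Protocol 4.4.1, 6.1 footnote 11 and 6.5.4; SAP Table 1 footnote 11. The start at 0 comes from Protocol Section 6.
- Draw described in SAP 11.2, B = 4 ± 0.5 = [3.5, 4.5].
- Window in SAP 20.1.2, W = [1, 5], assigned to the nominal time of 4 h.
- Planned cohort size, 20 (Protocol 10.1).

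**Step 1. Scheduled draw against the draw the SAP describes.** Overlap = min(1.5, 4.5) − max(0, 3.5) = 1.5 − 3.5 = −2.0. The intervals do not meet. The latest compliant draw comes 2.0 h before the SAP's draw may begin.

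**Step 2. Scheduled draw against the analysis window.** Overlap = min(1.5, 5) − max(0, 1) = 1.5 − 1 = 0.5 h. That is 0.5/1.5 = 33% of the compliant interval. The other 1.0/1.5 = 67% lies before the window opens. If a site does not use the +30 min allowance, only a draw at exactly 1.0 h enters the row.

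**Step 3. Timing error for samples that are kept.** It runs from 4 − 1.5 = 2.5 h to 4 − 1.0 = 3.0 h.

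**Step 4. Share left out.** The interval percentages in Step 2 become patient percentages only under an assumed pattern of draw times, since the documents give none. With one post-infusion sample per patient:

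| Assumed draw times | Left out of the row | Per cohort of 20 | Kept, but reported at 4 h |
|---|---|---|---|
| All at 1.0 to 1.5 h | 0% | 0 | 20 |
| Uniform over 0 to 1.5 h | 1.0/1.5 = 67% | 13.3 | 6.7 |
| All before 1 h | 100% | 20 | 0 |

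The first line would apply if chemistry were drawn with PK Sample 10, which Protocol Table 1 sets at "1 hour (+30 minutes) post final termination of the clevidipine infusion". The documents do not say that the two are drawn together.

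**Step 5. What can be said without draw times.** For a compliant draw at time t, t < 1 puts the sample outside W, and 1 ≤ t ≤ 1.5 puts it in the 4-hour row. No compliant sample is tabulated in a post-infusion row at its true time.

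**The case against.** The contradiction itself is not in dispute. Four objections bear on its reach and size.

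*The other windows may catch the early samples.* SAP 20.1.2 introduces the 24 to 96 h windows as covering the infusion, yet the last one runs to just under 106 h. Infusion is capped at 96 h and the 24-hourly draw has a tolerance of 1 h, so draws on infusion should end by about 97 h. The windows may therefore run on time since initiation and extend past the end of infusion. The ambiguity is real, but it does not rescue the row: a sample before 1 h is still absent from the post-infusion summary, and an off-drug value would instead enter an on-infusion row. If the infusion and the later draw both fall within 24 h, the closest-value rule would also prefer the post-infusion sample to the one due at termination.

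*The size is uninformative.* A range of 0% to 100% is not an estimate, and nothing in the documents supports uniform draw times. This stands, and the 67% is only an illustration. If chemistry is drawn with PK Sample 10, nothing is lost and the defect is the time label alone.

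*The consequence is small.* This largely stands. The study tests no formal hypothesis. Incidence of potentially clinically significant values counts any post-baseline value, and the listings hold all eCRF data. Chemistry during infusion, or at termination for infusions under 24 h, is still summarised. The primary safety endpoint also rests on adverse events. These points limit the seriousness without making the row correct.

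*A replacement window cut off at 1.5 h would lose late samples that the present 5 h limit keeps.* This is a fair point and is dealt with in the fix.

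**Conclusion.** The concern holds. The SAP describes, summarises and windows a 4-hour chemistry sample that neither the protocol nor the SAP's own schedule calls for, and it does not declare the difference. Any compliant sample is either missing from the post-infusion row or reported there 2.5 to 3.0 h late. That conclusion needs no assumption about draw times; it needs only the scheduled interval of 0 to 1.5 h. The statement that early samples enter no window at all also takes SAP 20.1.2 at its word that the other windows apply during infusion. How many patients would be left out is unknown.

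One descriptive row of a primary safety assessment is affected; the other laboratory outputs are not. It should be fixed, but it does not threaten the trial's main conclusions.

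**What to change.** The passages must be reconciled, in one of two ways.

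**If the protocol schedule stands:**
- Change the post-infusion time in SAP 11.2 and 11.2.2 to within 1 hour (+30 min) after termination.
- In SAP 20.1.2, open the window just after 0 h, run it through at least 1.5 h, and label it 1 hour post-infusion. State the upper limit. Keeping the present 5 h limit would retain late samples, and the existing closest-value rule can choose among several.
- State that a sample taken at termination of an infusion under 24 h stays in the during-infusion row, and that the 24 to 96 h windows exclude samples taken after the infusion has stopped.

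The cost is SAP wording and one programming window, with no new samples.

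**If a 4-hour sample was intended:** declare it in SAP Section 18, and change the protocol schedule and SAP Table 1 to match. This costs a protocol amendment and an extra or moved blood draw.

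Either way, settle it before the tables are programmed, so that nobody has to alter the window after seeing the data.

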### 11.2.1. Laboratory normalization

Because values of laboratory parameters in this study are provided from different local laboratories with different units and normal ranges, all numerical laboratory values will be converted to the conventional units and normalized to a standard set of reference/normal ranges [Chuang-Stein, 1992 and 2001]. The normalization process will be performed for each of the laboratory parameters. The method was adapted by a scale model described in Karvanen [2003] for values outside the normal local range and in the case of only one-sided defined standardized normal ranges. Details of the standardization process are described in the Appendix (Section 20.2). Normalized laboratory values will be used for the analyses of summary statistics, including relative and percent changes from baseline, described in Section 11.2.2.

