### 20.2. LABORATORY NORMALIZATION

Because values of laboratory parameters are provided from different study centers with different local laboratories, and with inconsistent units and normal ranges, all numerical laboratory values will be converted to conventional units and normalized to a standard set of reference/normal ranges by a location-scale model as described by Chuang-Stein (1992 and 2001). The method was adapted by a scale model described in Karvanen [2003] for values outside normal local range and in the case of only one-sided defined standardized normal ranges.

The normalization process will be performed for each laboratory parameter.

For numerical laboratory values, the normalized values will be proportional to the ratio of the widths of reference ranges and aligned with the corresponding lower limits. For example, let  $(L_S, U_S)$  denote the standard reference range. Let  $\varphi$  denote the laboratory value provided from Laboratory A, which is to be normalized. The normalized value,  $\varphi_S$ , can be derived from the formula,

$$\varphi_S = L_S + \beta \times (\varphi - L_A),$$

where (LA, UA) represents the reference range from Laboratory A and  $\beta$  denotes the ratio of the width from standard reference range over the width from Laboratory A (ie,  $\beta = (US - LS) / (UA - LA)$ ).

If one, say the lower, of the limits of a reference range is missing then the missing limit will be imputed according to the ratio of the limits from one of the closest reference ranges provided in this study. For example, let LM denote the missing lower limits from Laboratory M. Its corresponding higher limit, UM, is found to be closest to the upper limit, UC from Laboratory C among all the reference upper limits in the study. Then, LM will be imputed by the formula,

$$L_M = L_C \times (U_M / U_C),$$

where LC denotes the lower limit from Laboratory C. For cases where only the upper local limits are missing (i.e., the lower ones are not missing), the same imputation process will be performed. For cases where both limits of a local reference range are missing, the missing upper and lower limits will be imputed by the largest upper and lowest lower limit among all the observed local reference ranges, respectively.

For laboratory parameters with one-sided standard reference ranges the scale normalization formula (see formula 21 in Karvanen, 2003) will be applied as follows:

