Let  $L_S$  and  $U_S$  denote either side of the standard reference range.

Let w,  $L_w$  and  $U_w$  denote the value and either side of the local reference range.

If only  $L_S$  is available the normalized value will equal w \*  $L_S / L_w$ .

If only  $U_S$  is available the normalized value will equal w \*  $U_S / U_w$ .

For values outside the local reference ranges, the same formula will be applied to avoid complications by negative normalized values using the notation above:

If w is below  $L_w$ , then the normalized value will equal w \*  $L_S / L_w$ .

If w is above  $U_w$ , then the normalized value will equal w \*  $U_S / U_w$ .

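### Percent changes in laboratory values are computed on normalised values, which distorts their size for results inside a two-sided reference range

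*SAP*

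**What the plan says.** SAP 11.2.1 has every numerical laboratory result converted to conventional units and "normalized to a standard set of reference/normal ranges", because local laboratories differ in units and ranges. It then says: "Normalized laboratory values will be used for the analyses of summary statistics, including relative and percent changes from baseline". SAP 11.2.2 applies this to the tables: "Descriptive statistics for the values of serum chemistry as well as relative and percent changes from baseline will be summarized by time point".

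SAP 20.2 gives the method. For two-sided ranges, "the normalized values will be proportional to the ratio of the widths of reference ranges and aligned with the corresponding lower limits", where the multiplier β "denotes the ratio of the width from standard reference range over the width from Laboratory A". A pure scale factor replaces this "for values outside the normal local range and in the case of only one-sided defined standardized normal ranges". SAP 20.2 explains one of these exceptions: "For values outside the local reference ranges, the same formula will be applied to avoid complications by negative normalized values".

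Protocol 10.3.3.2 plans changes and percent changes from baseline and does not mention normalisation. SAP section 18, which lists departures from the protocol, names only vital signs.

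**The concern.** A percent change has meaning only relative to a fixed zero. The in-range formula in SAP 20.2 moves that zero, so the reported percent change depends on the local and standard ranges as well as on the patient's two results. The stated reason for normalising does not apply to this statistic: a constant unit factor cancels when two results from the same laboratory are divided.

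Protocol 3.3 lists safety by clinical laboratory parameters among the primary endpoints. The serum chemistry tables are the planned summary of laboratory change, and no table of raw percent change is specified. A programmer who follows the SAP exactly would therefore produce tables whose percent changes cannot be read at face value for some parameters.

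**Working it through.** **Inputs.** The formulas are those of SAP 20.2. The plan gives no figure to reproduce and no numerical local or standard limits; Table 3 uses LLN and ULN as symbols only. Every range below is therefore an assumption.

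**Notation.** Local range (L_A, U_A); standard range (L_S, U_S); β = (U_S − L_S)/(U_A − L_A); raw baseline x1; raw follow-up x2.

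**Both results in range, two-sided limits.**
- Normalised value: L_S + β(x − L_A).
- Raw relative change: (x2 − x1)/x1.
- Normalised relative change: β(x2 − x1)/(L_S + β(x1 − L_A)).
- Ratio, normalised to raw: R = x1/(x1 + L_S/β − L_A).
- R = 1 only if L_S = β·L_A, that is L_S·U_A = L_A·U_S. The limits must be proportional, or both lower limits zero.

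**Branches that keep percent change exact.** With a one-sided standard range, or with both results outside the local range on the same side, both are multiplied by one constant and R = 1. (Below the range this requires a standard lower limit above zero.) The pieces of the rule join at the local limits and each rises with x, so with one local range the direction of change is kept.

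**Examples (all ranges assumed).**

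| Local range | Standard range | Raw results | Raw change | Normalised results | Reported change | R |
|---|---|---|---|---|---|---|
| 0.2–0.8 | 0.6–1.2 | 0.4 → 0.6 | +50% | 0.8 → 1.0 | +25% | 0.50 |
| 0.6–1.2 | 0.2–0.8 | 0.8 → 1.2 | +50% | 0.4 → 0.8 | +100% | 2.00 |
| 3.5–6.0 | 3.5–5.0 | 4.0 → 5.0 | +25% | 3.8 → 4.4 | +15.8% | 0.63 |
| 130–150 | 135–145 | 138 → 142 | +2.9% | 139 → 141 | +1.4% | 0.50 |
| 135–145 | 130–150 | 138 → 142 | +2.9% | 136 → 144 | +5.9% | 2.03 |
| 5–45 | 10–40 | 20 → 90 (in range to above) | +350% | 21.25 → 80 | +276% | 0.79 |
| 10–40 | 20–80 (proportional) | 20 → 30 | +50% | 40 → 60 | +50% | 1.00 |
| 5–45 | 10–40 | 90 → 180 (both above) | +100% | 80 → 160 | +100% | 1.00 |

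**Range of R.** Each local limit is allowed to differ from the standard limit by up to the stated percentage, in either direction, with baseline at the middle of the local range. At mid-range R reduces to β × (local midpoint)/(standard midpoint).

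| Standard range (ULN/LLN) | Limits within | R |
|---|---|---|
| 10–40 (4) | 10% | 0.91 to 1.13 |
| 0.6–1.2 (2) | 10% | 0.79 to 1.38 |
| 3.5–5.0 (1.43) | 2% | 0.90 to 1.12 |
| 3.5–5.0 (1.43) | 10% | 0.65 to 2.27 |
| 135–145 (1.07) | 1% | 0.78 to 1.39 |
| 135–145 (1.07) | 2% | 0.64 to 2.27 |

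Check of the last row:
- Local 132.3–147.9: β = 10/15.6 = 0.641, and R = 0.641 × 140.1/140 = 0.64.
- Local 137.7–142.1: β = 10/4.4 = 2.273, and R = 2.273 × 139.9/140 = 2.27.

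Narrow ranges far from zero are sensitive because a 2% shift of each limit is large relative to a width of 10.

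**After the fix.** On raw values in common units from one laboratory, R = 1.00 in every row.

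**The case against.** The case for leaving the plan alone is that these tables are descriptive, with no hypothesis test. SAP section 4 promises listings of all eCRF data, and SAP 11.2.2 lists raw beside standardised values for patients with potentially clinically significant (PCS) results, so raw values remain visible. PCS incidence is a separate analysis that uses no percent change. There are only two US centres (Protocol 4.1), so limits may be similar, and where the relative distortion is largest, as for sodium, it is about three percentage points or less in the examples shown. All of this limits the consequence, but listings do not correct a summary table.

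Four stronger readings are tempting, and the documents do not support them.
- *No reported laboratory percent change is valid.* The scale branches and proportional ranges keep it exact, and the plan does not say which parameters have two-sided standard ranges.
- *Reported changes will be half or double the true ones.* Such ratios are attainable, but only under limits that the documents do not give.
- *The result reflects the standard range rather than the patient.* It depends on both.
- *The rule for missing limits can only hide abnormalities.* When both local limits are absent, "the missing upper and lower limits will be imputed by the largest upper and lowest lower limit among all the observed local reference ranges". That is the widest observed range. A laboratory whose true range extends beyond it could have a normal result flagged, and a baseline result pulled into range puts the patient in the denominator for new PCS values, where a later value can count as a new case. The documents give no indication of how often the rule would be used.

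**Conclusion.** The point holds for results inside a two-sided local range, and for pairs in which one result is inside and the other outside. For these, SAP 11.2.1 combined with the formula in SAP 20.2 gives a percent change that differs in size from the raw one unless the limits are proportional or both lower limits are zero. That follows from the algebra and needs no assumption about limits.

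The size does rest on assumptions. It runs from roughly a tenth for wide ranges with similar limits to about two-fold for narrow ranges or large mismatches. The SAP does not say whether the standard ranges are age-specific. With enrolment from preterm newborns to adolescents, a single standard set compared with age-specific local ranges could produce mismatches larger than those between two laboratories, but that too is an assumption.

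The error affects descriptive safety tables only; efficacy analyses and sample size are untouched. It is worth correcting because the reported statistic is wrong as specified and the correction is cheap.

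**What to change.** In SAP 11.2.1 and 11.2.2, compute percent (relative) change from baseline on raw values converted to conventional units. Keep normalised values for level summaries, absolute changes and PCS flags. Define relative change, which the SAP names beside percent change without explaining it. Add a footnote to each table saying which values it uses.

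The cost is a change of SAP wording and a second stream of values in the laboratory tables, so a reader could not rebuild the percent changes from the normalised levels shown beside them; hence the footnote. Unit factors cancel only when baseline and follow-up come from the same laboratory and method, so pairs measured at different laboratories should be identified in the listing.
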